10.3 Appendix 3: Treatment States

10.3.1 Treatment States

Assessments and events will be classified according to time of occurrence relative to the start and/or stop date and time of the study treatment.

Treatment State	Definition
Pre-Treatment	Date and time < Study Treatment Start Date and time
On-Treatment	If onset date is on or after treatment start date and time & on or before the treatment stop date and time Study Treatment Start Date and time \leq Date and time \leq Study Treatment Stop Date and time
Post-Treatment	If onset date and time is after the treatment stop date and time Date and time > Study Treatment Stop Date and time
AE Onset Time Since First Dose (Days)	If Treatment Start Date > AE Onset Date = AE Onset Date - Treatment Start Date If Treatment Start Date \leq AE Onset Date = AE Onset Date - Treatment Start Date +1 Missing otherwise
AE Duration (Days)	AE Resolution Date – AE Onset Date + 1
AE Drug-related	If relationship is marked ‘YES’ on eCRF or value is missing.

NOTES:

- If the study treatment stop date is missing then the AE will be considered to be On-Treatment.

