4. STUDY DESIGN

4.1. Part A (Single Dose)

Figure 1 Part A Schematic

★ Dose escalation meeting

- o One of the dosing periods will be a food effect group – the dose will be determined based on data from previous cohorts
- o There will be a 2 week washout between doses initially but the washout period may be modified depending on emerging data from previous cohorts.
- o Cohorts 1 and 2 will be dosed sequentially. If it is considered desirable to dose Cohorts 1 and 2 in an overlapping/interlocking fashion, approval will be sought from the Regulatory Agency first.

Up to two cohorts will be included in the single dose part (Part A). Each cohort will participate in up to 4 treatment (dosing) periods (including a food effect treatment period). Initially, there will be a 14 day wash out period for individual subjects between each dose level which is considered sufficient in light of the predicted half-life of GSK3036656 [on average, approximately 30 hours (range: 12 to 72 hours) based on the various preclinical extrapolation methods], however this may be revised once relevant PK data is obtained. Nine subjects per cohort will be enrolled and randomised to ensure adequate safety, tolerability and PK information is gained and a balanced randomisation is achieved across all treatment (dosing) periods.

During each treatment (dosing) period, GSK3036656 will be administered to 6 subjects and placebo will be administered to 3 subjects. As this is a FTIH study, each treatment (dosing) period will be staggered over 2 days. On Day 1 of each dose level, one subject will receive GSK3036656 and one subject will receive placebo. The remaining subjects within the dosing group will be dosed one day later provided satisfactory safety and tolerability is demonstrated for the subjects dosed on Day 1. A treatment (dosing) period does not have to be staggered if the dose administered is equal to or lower than a dose that has been already tested and found to be safe and well tolerated.

Subjects will attend the unit on Day -1 for assessments and a meal. The subjects will then fast overnight (at least 8 hours) and be dosed the following morning (Day 1). Dosing with food may also be done in Part A once results from the food effect analysis are available. Dividing the total dose for the treatment (dosing) period into 2 or 3 smaller doses administered within 24 hours may also be done. The decision to divide the total dose into

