8.1. Overview of Planned Adverse Events Analyses

Adverse Events will be coded using Medical Dictionary for Regulatory Activities (MedDRA) central coding dictionary and summarized by dose group.

Counting of AEs will be based on the number of subjects – not the number of AEs. For example if a subject experiences the same AE (i.e. same preferred term) more than once, they are counted only once under the count for the preferred term. If a subject experiences more than one AE in a particular SOC, they will only be included once in the count for the SOC, but will appear in the count for each appropriate preferred term within the SOC. Therefore, the sum of the numbers of subjects with each preferred term event within a SOC may exceed the total number of subjects with at least one event. For the summary of AEs by maximum intensity, subjects who experience the same event several times with different intensity will only be counted once with the maximum intensity.

[Table 6](#) provides an overview of the planned analyses, with further details of data displays being presented in [Appendix 10: List of Data Displays](#).

Table 6 Overview of Planned Adverse Event Analyses

Endpoint / Parameter/ Display Type	Absolute		
	Summary		Individual
	T	F	L
Adverse Events (AEs)			
All AE's	Y		Y
Serious AE's	Y		Y
Drug Related AEs	Y		Y
AE's leading to withdrawal	Y		Y
Common (>=5% in any treatment group) Non-serious AEs by SOC and PT – number of subjects and occurrences	Y		
Serious Adverse Events by System Organ Class and Preferred Term (Number of Subjects and Occurrences)	Y		
Relationship Between System Organ Class And Verbatim Text			Y
Subject Numbers for Individual Adverse Events			Y

NOTES:

- T = Table, F = Figures, L = Listings, Y = Yes display generated
- Summary = Represents TF related to any summaries (i.e. descriptive statistics) of the observed raw data.
- Individual = Represents FL related to any displays of individual subject observed raw data.

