10.5.2 Study Population

Demographics

Age

- GSK standard IDSL algorithms will be used for calculating age where birth date will be imputed as follows:
 - Any subject with a missing day will have this imputed as day ‘15’.
 - Any subject with a missing date and month will have this imputed as ‘30th June’.
- Birth date will be presented in listings as ‘YYYY’.

Body Mass Index (BMI)

- Calculated as **Weight (kg) / [Height (m)]²**

Extent of Exposure

- Number of days of exposure to study drug will be calculated based on the formula:
Duration of Exposure in Days = Treatment Stop Date – (Treatment Start Date) + 1
- Subjects who were randomized but did not report a treatment start date will be categorised as having zero days of exposure.
- The cumulative dose will be based on the formula:

Cumulative Dose = Sum of (Number of Days x Total Daily Dose)

- If there are any treatment breaks during the study, exposure data will be adjusted accordingly.

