10.6.2.1 Handling of Missing Dates

Element	Reporting Detail
General	Partial dates will be displayed as captured in subject listing displays.
Adverse Events	
 The eCRF allows for the possibility of partial dates (i.e., only month and year) to be recorded for AE start and end dates; that is, the day of the month may be missing. In such a case, the following conventions will be applied for calculating the time to onset and the duration of the event: 
 Missing Start Day: First of the month will be used unless this is before the start date of investigational product; in this case the study treatment start date will be used (and hence the event is considered

Element	Reporting Detail
	
On-treatment as per Appendix 3: Treatment States and Phases).
 
 • Missing Stop Day: Last day of the month will be used, unless this is after the stop date of study treatment; in this case the study treatment stop date will be used. • Completely missing start or end dates will remain missing, with no imputation applied. Consequently, time to onset and duration of such events will be missing. • AEs with entirely missing or unknown start dates will be assumed to be on-treatment for reporting. • AEs with missing end dates are not anticipated to affect reporting.

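### The on-treatment state ends at an undefined treatment stop with no post-dose window, so AE states, imputed AE durations and crossover dose attribution lack a sound basis

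*SAP*

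**What the plan says.** SAP 10.3.1 sorts events by their time relative to the start and stop of study treatment. An event is On-Treatment under the rule "If onset date is on or after treatment start date and time & on or before the treatment stop date and time" and Post-Treatment under the rule "If onset date and time is after the treatment stop date and time". No follow-up days or half-lives are added to the stop. The one note to the table covers a missing stop: "If the study treatment stop date is missing then the AE will be considered to be On-Treatment".

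The SAP does not define the stop date and time. In Part A a subject can have up to four dosing periods (Protocol 4.1), and the SAP does not say whether start and stop are set for each period or once per subject. The closest thing to a definition is the exposure formula in SAP 10.5.2: "Duration of Exposure in Days = Treatment Stop Date – (Treatment Start Date) + 1".

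The stop date has a second use. SAP 10.6.2.1 and 10.6.2.2 impute a partial AE stop date as the end of the month or year, and replace it with the treatment stop date if it falls later than that. SAP 10.6.2.1 also states: "AEs with entirely missing or unknown start dates will be assumed to be on-treatment for reporting".

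SAP 8.1 has AEs coded with the MedDRA "central coding dictionary and summarized by dose group". SAP 10.4.1 lists the display columns as placebo plus up to eight dose levels in Part A.

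**The concern.** AEs belong to the first primary endpoint. In a single-dose study, the events of interest come in the hours and days after dosing. A window that ends at the last dose puts those hours outside the treatment state. In Part B it excludes the time just after the final dose, and Protocol 6.3.2 expects exposure to be highest on the last dosing day.

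Part A is also a crossover with placebo, so each AE has to be placed in one dose column. A treatment state defined by period would do this. The state as written does not, and no other section gives the rule.

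Using the stop date as a cap on AE end dates adds a derivation fault: an AE can be recorded as ending before it began.

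**Working it through.** **Which stop fits the SAP.** SAP 10.5.2 gives exposure days = stop − start + 1, and cumulative dose = days × total daily dose.
- Single dose with stop = dosing date: 0 + 1 = 1 day and one dose, which is correct.
- Stop moved to the 14-day follow-up: 14 + 1 = 15 days and 15 times the dose given, which is wrong.

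So stop = last dose is the reading that makes the exposure formula work. It remains an inference.

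**Part A, read per period, one undivided dose.** Start = stop = 0 h, so On-Treatment requires 0 ≤ onset ≤ 0. Onsets at 0.25, 0.5, 1, 2, 6, 12, 24, 48 and 72 h and at 14 days are all Post-Treatment. Protocol 4.1 allows the dose to be divided within 24 hours. If the last fraction is given at 12 h (an assumption), onsets up to 12 h are On-Treatment and later ones are not.

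**Part A, read per subject.** Inputs are the washout in Protocol 4.1, "Initially, there will be a 14 day wash out period for individual subjects between each dose level", and follow-up about 14 days after the last dose. For k periods, the On-Treatment window is 14(k − 1) of 14k days:
- k = 1: 0 of 14 days (0%)
- k = 2: 14 of 28 (50%)
- k = 3: 28 of 42 (67%)
- k = 4: 42 of 56 (75%)

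This time includes washout and any interval that follows a placebo dose. Everything after the last dose is excluded, whether that dose was active or placebo.

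**Part B.** With dosing complete on Days 1 to 14 and follow-up on Day 28, the window is 14 − 1 = 13 of 28 − 1 = 27 days (48%).

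**Drug still present when the window closes.** Protocol 4.1 predicts a half-life of about 30 h (range 12 to 72 h). Assuming mono-exponential decline, the fraction remaining is 0.5^(t / half-life):
- At 24 h: 0.5^(24/30) = 57% (range 25% to 79%)
- At 72 h: 0.5^(72/30) = 19% (range 2% to 50%)

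This applies to active doses only. One third of Part A subject-periods are placebo (3 of 9 subjects).

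**Imputed AE stop dates.** As an illustration, take one dose on 10 June, AE onset on 12 June, and AE stop recorded only as June. The end-of-month value, 30 June, is later than the treatment stop, so 10 June replaces it. SAP 10.3.1 gives duration = resolution − onset + 1 = 10 − 12 + 1 = −1 day. With onset on 11 June it is 10 − 11 + 1 = 0 days. Read per subject, the same fault arises for AEs that start after the last dose.

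**The case against.** A reader might infer that no Part A event can ever be On-Treatment, or that Part A events drop out of the primary safety results. The documents support neither.

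- The stop is never defined as the time of the last dose. If it were held as a date without a time, events later on the dosing day would be On-Treatment, including those on Day 14 of Part B.
- Under the per-subject reading, most of a four-period subject's time is On-Treatment.
- A divided dose gives a window of non-zero length.
- A missing treatment stop, a wholly missing onset date, or a partial onset date imputed to treatment start each makes an AE On-Treatment by convention.
- The AE displays in SAP 8.1 and 10.10.7 cover all, serious, drug-related, withdrawal and common events, and none is titled as on-treatment only. Drug-relatedness comes from the eCRF field, not from the state. Total AE counts therefore stand.

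It can also be said that SAP 10.4.3 reports data by the actual treatment received, so attribution is not wholly unaddressed. That settles planned versus actual treatment. It does not say which of up to four treatments an AE in washout belongs to. On its own, this gap would be missing detail.

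These points limit the reach of the concern but do not remove it. The window is a stated rule with no post-dose extension, both ways of setting start and stop give an unsuitable state in Part A, and the cap on AE stop dates can produce impossible durations.

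**Conclusion.** The concern holds in a limited form. The harm is to treatment-state labels, imputed AE durations and the basis for placing crossover AEs in a dose column. It is not a loss of AEs from the planned tables.

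The size depends on a choice the SAP leaves open. Per period, the window after an undivided dose has zero length for every AE with a complete onset date and time, across at most 18 × 4 = 72 Part A subject-periods. Per subject, it covers 0% to 75% of the time from first dose to follow-up, including washout and placebo time. In Part B it covers about 48%. The number of AEs affected cannot be derived from the documents.

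These results assume that stop means last dose, that washouts and follow-up last 14 days, and that all 14 Part B doses are given. The negative durations arise only for AEs with a partial stop date whose onset is after the treatment stop date.

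**What to change.** In SAP 10.3.1, define the state per dosing period. On-Treatment should run from dosing until immediately before the next period's dose or, for the last Part A period and for Part B, through the follow-up visit. State that each AE is assigned to the most recent treatment and dose received at onset. In SAP 10.6.2.1 and 10.6.2.2, cap imputed AE stop dates at the end of that window, and never before onset, instead of at the treatment stop date. The conventions for missing and partial onset dates will then also need to say which period such an AE belongs to.

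A fixed or half-life-based lag would be another workable convention for the window. What matters is that one is written down before unblinding. The cost is SAP wording and a change to the AE derivation program. No new data, visits or protocol changes are needed.

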10.4 Appendix 4: Data Display Standards & Handling Conventions

10.4.1 Study Treatment & Display Descriptors:

Treatment Group Descriptions			
RandAll NG		Data Displays for Reporting	
Part	Code	Description	Description ^[1]
A	P	Placebo	Placebo
A	D1	GSK3036656 Dose 1	Dose X mg
A	D2	GSK3036656 Dose 2	Dose X mg
A	D3	GSK3036656 Dose 3	Dose X mg
A	D4	GSK3036656 Dose 4	Dose X mg
A	D5	GSK3036656 Dose 5	Dose X mg
A	D6	GSK3036656 Dose 6	Dose X mg
A	D7	GSK3036656 Dose 7	Dose X mg
A	D8	GSK3036656 Dose 8	Dose X mg
B	P	Placebo	Placebo
B	R1	GSK3036656 Repeat Dose 1	Repeat Dose X mg
B	R2	GSK3036656 Repeat Dose 2	Repeat Dose X mg
B	R3	GSK3036656 Repeat Dose 3	Repeat Dose X mg
B	R4	GSK3036656 Repeat Dose 4	Repeat Dose X mg

NOTES:

The decision to proceed to each subsequent dose level will be made by the Dose Escalation Committee (DEC)

Note, in tables, figures and listings, treatments should be presented with placebo first, then in order of increasing dose within each study part.

1. 'Dose X' to be replaced by actual dose.

10.4.2 Baseline Definition & Derivations

10.4.2.1 Baseline Definitions

For all endpoints the baseline value will be the latest pre-dose assessment.

Unless otherwise stated, the mean of replicate assessments at any given time point will be used as the value for that time point.

If the latest pre-dose assessment is missing then the previous assessment time point would be considered as baseline where possible (i.e. if Day 1 (Pre-dose) is missing the Day -1 will be used).

10.4.2.2 Derivations and Handling of Missing Baseline Data

Definition	Reporting Details
Change from Baseline	= Post-Dose Visit Value – Baseline
% Change from Baseline	= 100 x [(Post-Dose Visit Value – Baseline) / Baseline]

NOTES :

- Unless otherwise specified, the baseline definitions specified in Section 10.4.2.1 Baseline Definitions will be used for derivations for endpoints / parameters and indicated on summaries. Unless otherwise stated, if baseline data is missing or post-dose data is missing no derivation will be performed and (%) change from baseline will be set to missing.
- The baseline definition will be footnoted on all change from baseline displays.

10.4.3 Reporting Process & Standards

Reporting Process	
Software	

 The currently supported versions of SAS software will be used. 	
Reporting Area	
HARP Server	: UK1SALX00175
HARP Area	: arenv/arprod/GSK3036656/201040/final
QC Spreadsheet	: arenv/arwork/GSK3036656/201040/final/documents
Analysis Datasets	

 Analysis datasets will be created according to CDISC standards (SDTM IG Version 3.1.3 & AdaM IG Version 1.0). For creation of AdaM datasets (ADCM/ADAE), the same version of dictionary datasets will be implemented for conversion from SI to SDTM. 	
Generation of RTF Files	

 RTF files will be generated for SAC. 	

Reporting Standards	
General	

 The current GSK Integrated Data Standards Library (IDSL) will be applied for reporting, unless otherwise stated: 
 4.03 to 4.23: General Principles 5.01 to 5.08: Principles Related to Data Listings 6.01 to 6.11: Principles Related to Summary Tables 7.01 to 7.13: Principles Related to Graphics 	
Formats	

 All data will be reported according to the actual treatment the subject received unless otherwise stated. GSK IDSL Statistical Principles (5.03 & 6.06.3) for decimal places (DP's) will be adopted for reporting of data based on the raw data collected. Numeric data will be reported at the precision collected on the eCRF. The reported precision from non eCRF sources will follow the IDSL statistical principles but may be adjusted to a clinically interpretable number of DP's. 	
Planned and Actual Time	

 Reporting for tables, figures and formal statistical analyses : 
 Planned time relative to dosing will be used in figures, summaries, statistical analyses and calculation of any derived parameters, unless otherwise stated. The impact of any major deviation from the planned assessment times and/or scheduled visit days on the analyses and interpretation of the results will be assessed as appropriate. Reporting for Data Listings: 
 Planned and actual time relative to study drug dosing will be shown in listings (Refer to IDSL Statistical Principle 5.05.1). Unscheduled or unplanned readings will be presented within the subject's listings. Visits outside the protocol defined time-windows (i.e. recorded as protocol deviations) will be included in listings but omitted from figures, summaries and statistical analyses. 	
Unscheduled Visits	

 Unscheduled visits will not be included in summary tables. Unscheduled visits will not be included in figures. All unscheduled visits will be included in listings. 	
Descriptive Summary Statistics	
Continuous Data	Refer to IDSL Statistical Principle 6.06.1
Categorical Data	N, n, frequency, %
Reporting of Pharmacokinetic Concentration Data	
Descriptive Summary Statistics	Refer to IDSL Statistical Principle 6.06.1 and Standards for the Transfer and Reporting of PK Data using HARP.

Reporting Standards	
	For NQ values, refer to GUI_51487.
Reporting of Pharmacokinetic Parameters	
Descriptive Summary Statistics. (Log _e Transformed)	N, n, geometric mean, 95% CI of geometric mean, standard deviation (SD) of log transformed data and between subject geometric coefficient of variation (CVb (%)) will be reported. CVb (%) = $\sqrt{(\exp(SD^2) - 1) * 100}$ [NOTE: SD = SD of log _e transformed data]
Parameters Not Being Log _e Transformed	Tmax, t _{1/2}
Summary Tables	Cmax, t _{max} , AUC(0- τ), AUC(0-t), AUC (0- ∞), AUC (Ro), RCmax, C τ , t _{1/2} , Rss, Ae, fe, CLR, as data permit
Listings	Include PK Parameters Cmax, t _{max} , AUC(0- τ), AUC(0-t), AUC (0- ∞), AUC (Ro), RCmax, C τ , t _{1/2} , Rss, Ae, fe, CLR, as data permit
Graphical Displays	

 Refer to IDSL Statistical Principles 7.01 to 7.13 and Standards for the Transfer and Reporting of PK Data using HARP. 	

10.5 Appendix 5: Derived and Transformed Data

10.5.1 General

Multiple Measurements at One Time Point

- Mean of the measurements will be calculated and used in any derivation of summary statistics but if listed, all data will be presented.
- If there are two values within a time window the value closest to the target day for that window will be used. If values are the same distance from the target then the mean will be taken.
- Subjects having both High and Low values for Normal Ranges at any post-baseline visits for safety parameters will be counted in both the High and Low categories of “Any visit post-baseline” row of related summary tables. This will also be applicable to relevant Potential Clinical Importance summary tables.

Study Day

- Calculated as the number of days from Treatment start date :
 - Ref Date = Missing → Study Day = Missing
 - Ref Date < Treatment start Date → Study Day = Ref Date – Treatment start Date
 - Ref Date ≥ Treatment start Date → Study Day = (Ref Date – Treatment start Date) + 1

10.5.2 Study Population

Demographics

Age

- GSK standard IDSL algorithms will be used for calculating age where birth date will be imputed as follows:
 - Any subject with a missing day will have this imputed as day ‘15’.
 - Any subject with a missing date and month will have this imputed as ‘30th June’.
- Birth date will be presented in listings as ‘YYYY’.

Body Mass Index (BMI)

- Calculated as **Weight (kg) / [Height (m)]²**

Extent of Exposure

- Number of days of exposure to study drug will be calculated based on the formula:
Duration of Exposure in Days = Treatment Stop Date – (Treatment Start Date) + 1
- Subjects who were randomized but did not report a treatment start date will be categorised as having zero days of exposure.
- The cumulative dose will be based on the formula:

Cumulative Dose = Sum of (Number of Days x Total Daily Dose)

- If there are any treatment breaks during the study, exposure data will be adjusted accordingly.

10.5.3 Safety**Laboratory Parameters**

- If a laboratory value which is expected to have a numeric value for summary purposes, has a non-detectable level reported in the database, where the numeric value is missing, but typically a character value starting with '<x' or '>x' (or indicated as less than x or greater than x in the comment field) is present, the number of decimal places in the observed values will be used to determine how much to add or subtract in order to impute the corresponding numeric value.
 - Example 1: 2 Decimal Places = '<x' becomes x - 0.01
 - Example 2: 1 Decimal Places = '>x' becomes x + 0.1
 - Example 3: 0 Decimal Places = '<x' becomes x - 1

